2.2 Secondary Objectives

- 1. To assess the impact of various funding models on vaccination coverage.
- 2. To evaluate a pharmacy-based strategy for recruiting participants for a patient-reported active adverse event following immunization surveillance system.

2.3 Primary Hypothesis:

 Vaccine coverage with all studied vaccines (high dose TIV, meningococcal B vaccine, meningococcal ACWY vaccine, Tdap, herpes zoster vaccine, and travel health vaccines) will increase significantly after implementation of the bundled pharmacist-delivery strategy. A significant increase will be defined as an increase of ≥10% vaccine coverage from preintervention levels.

2.4 Secondary Hypotheses:

- 1. The cost of a vaccine is a key factor in the individual's decision to be vaccinated. It is expected that vaccinations provided at no or minimal charge will have higher uptake than those that require more financial resources to obtain.
- 2. Knowledge about the vaccines studied is low among the general public, but higher among practitioners. There is a high level of support among both the public and health care providers for pharmacists as immunizers. Knowledge and support amongst both providers and the public will increase after implementation of the program.

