Pharmacy databases will be used to determine the number of doses administered to individuals relative to the total number of clients in the pharmacy database in the eligible age range. The total number of doses administered by pharmacists (from their database) plus the number administered by family physicians, through study-specific reciprocal notification forms, will also be calculated and compared to

ROMEO File #: 1021559

the Statistics Canada population age-specific census data for the community will also be calculated. The study-specific system of reciprocal notification forms for family physicians will be implemented so that it is similar to that used for publicly funded routine pediatric vaccines. Another estimate of vaccine coverage will be vaccine doses distributed to pharmacies in the participating communities (obtained from the manufacturer and Public Health) relative to the eligible population based on Statistics Canada census data from 2016. Specific questions about receipt of target vaccines will be added to the KABB survey that will be administered pre- and post-intervention. These questions will be modeled on a 2014 study performed by the Vaccine Evaluation Center (Schneeberg, 2014). The KABB survey will also include specific questions about willingness to pay to inform decisions about co-payment funding models for recommended adult vaccines.

Outcomes

As a result of this study:

- 1. Population specific vaccine coverage will be documented before and after program implementation interventions.
- 2. The proportion of the population in intervention districts whose supplementary health benefit plans cover studied vaccines will be identified.
- 3. The public willingness to pay and co-pay for studied vaccines will be better known and understood.

For specific outcomes related to each targeted vaccine, see appendices.

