6 OUTCOME MEASURES AND STATISTICAL METHODS

6.1 Outcomes/analysis plan/sample size/statistics

6.1.1 Primary Outcomes

- 1. Population specific vaccine coverage before and after bundled pharmacist-delivery intervention.
- 2. Proportion of population in intervention districts whose supplementary health benefit plans cover studied vaccines.
- 3. Public KABB about vaccine preventable diseases and related vaccines before and after program implementation interventions.
- 4. Public willingness to pay and co-pay for studied vaccines.
- 5. Health care KABB regarding pharmacist- delivered vaccine programs.
- 6. Public and health care provider satisfaction with various models of vaccine program delivery.

ROMEO File #: 1021559

Proportions of influenza vaccine recipients who register for CANVAS and who complete the online AEFI survey in intervention versus control communities.

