
2. AEFI Surveys. Point estimates and exact binomial 95% confidence intervals will be calculated for the proportion of influenza vaccine recipients who register for the AEFI survey and the proportion who complete the survey. Descriptive statistics will be used to compare proportions registering and completing the survey among intervention versus control communities. Overall frequency of severe adverse events and the frequency of specific health events (e.g., injection site pain that prevents daily activities) will be calculated. The frequency of severe AEFI will be compared by influenza vaccine type [e.g., QIV, TIV] and by season (i.e., 2016-17 and 2017-18). The frequency of health events after vaccination will be compared to the background event rate estimated by the control survey.

3. Vaccine coverage. Pharmacy databases will be used to determine the number of doses administered to individuals eligible for receipt of vaccine relative to the total number of clients in the pharmacy database in the eligible age range. A second estimate of coverage will be

ROMEO File #: 1021559

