determined by physician billing data and public health provision of vaccine to physicians relative to the Statistics Canada population age specific census data for that community. A study-specific system of reciprocal notification forms for family doctors will be implemented that is similar to that used for publicly funded routine vaccines. A third estimate of vaccine coverage will be vaccine doses distributed in the participating communities (obtained from the manufacturer) relative to the eligible population based on Statistics Canada census data (2011 and 2016 when available). The fourth estimate of vaccine coverage will be derived from the pre- and postprogram public survey. Binomial point estimates and confidence intervals will be made for vaccine coverage rate within site, and coverage will be compared between and among sites using confidence intervals for the difference of binomial proportions, Fisher's exact tests, and logistic regression. Using a margin of superiority of 10%, when comparing two coverage proportions within site or between sites, a sample size of 298 per group gives 80% power to conclude in favor of superiority when the true difference in proportions is at least 20%, and a sample size of 1209 per group provides 80% power when the true difference in proportions is at least 15%, assuming independent responses. However, it is anticipated that there will be dependence within the family unit regarding the decision to be vaccinated, in which case the precision on the binomial point estimate, and thereby, the required sample size, depends on the size of the family unit and the intraclass correlation. Assuming the family unit to consist of two adults, and under the worst-case scenario in which the decision on vaccination is fully concordant for the two family members, the required sample size per group to detect a specified difference is doubled, to 596 (2418) when the true difference is at least 20% (15%). Estimates of the intraclass correlation will be calculated using data from pharmacy databases and from the public survey portion of the study, and these will be used to adjust confidence intervals and test statistics to accommodate within family dependence (Donner, Brikett, & Buck, 1981).

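### Section 6.2's second coverage estimate leaves out the pharmacist doses that Section 3.1 counts, and the two sections also define distributed doses differently; they should be reconciled

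*Combined protocol and SAP*

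**What the plan says.** Section 6.1.1 lists coverage first among the primary outcomes: "Population specific vaccine coverage before and after bundled pharmacist-delivery intervention". The Synopsis defines coverage as people vaccinated over people eligible, whoever gives the dose. Section 2.3 sets the target: "A significant increase will be defined as an increase of ≥10% vaccine coverage from preintervention levels".

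Sections 3.1 and 6.2 each describe how coverage will be measured.

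- **Pharmacy database.** The two sections agree. In the words of 6.2, it is "the number of doses administered to individuals eligible for receipt of vaccine relative to the total number of clients in the pharmacy database", within the eligible age range.
- **Census-based count of doses.** The numerator in 3.1 is: "The total number of doses administered by pharmacists (from their database) plus the number administered by family physicians, through study-specific reciprocal notification forms", set against the community's age-specific census population. In 6.2 the second estimate is "determined by physician billing data and public health provision of vaccine to physicians relative to the Statistics Canada population age specific census data". The next sentence of 6.2 adds: "A study-specific system of reciprocal notification forms for family doctors will be implemented". It does not place those forms in any numerator and does not mention pharmacist doses.
- **Distributed doses.** Section 3.1 uses "vaccine doses distributed to pharmacies in the participating communities (obtained from the manufacturer and Public Health"), over the 2016 census. Section 6.2 says: "A third estimate of vaccine coverage will be vaccine doses distributed in the participating communities (obtained from the manufacturer"), over the 2011 census and the 2016 census once available. The Synopsis gives 2015 as the census year for the denominator.
- **Public survey.** Both sections use it, before and after the program.

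The visible text does not say which estimate decides the primary outcome. Section 3.1 sends vaccine-specific outcomes to appendices that were removed from the public copy.

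**The concern.** The intervention is a pharmacist-delivery strategy, so the doses it is meant to add are largely pharmacist doses. A numerator built only from physicians' billing and the vaccine supplied to physicians excludes them. It is therefore not coverage as the Synopsis defines it. Two analysts, one working from 3.1 and the other from 6.2, could report different changes for the same community and the same events, and both would call the result a census-based coverage estimate. If a program succeeded by drawing people from physicians' offices to pharmacies, the 6.2 figure could move against the truth.

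The distributed-dose mismatch is of the same kind. A count of doses shipped to pharmacies and a count of doses shipped to the whole community answer different questions. Manufacturer data alone may also give a different total from manufacturer and Public Health data together.

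**Working it through.** **The plan's own figures.** Section 6.2 gives 298 per group (true difference 20%) and 1209 per group (true difference 15%), for a 10% superiority margin and 80% power. It does not state alpha, sidedness or base rates. With n = [p1(1−p1) + p2(1−p2)] × (z_alpha + z_0.80)² / (difference − 0.10)², one-sided alpha 0.05 and proportions centred on 0.5:

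- 0.40 v 0.60: 0.48 × 6.183 / 0.01 = 297 after rounding up (stated 298).
- 0.425 v 0.575: 0.48875 × 6.183 / 0.0025 = 1209 (stated 1209).

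Doubling 298 and 1209 gives the plan's 596 and 2418. These figures do not bear on the mismatch. They do show that 6.2 treats its 10% margin as a difference in proportions, so percentage points are used below.

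**The definitions side by side.**

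| Element | Section 3.1 | Section 6.2 |
|---|---|---|
| Census-based numerator | pharmacist + family-physician doses | physician sources only |
| Physician source | notification forms | billing and public health supply; forms mentioned but not tied to a numerator |
| Distributed doses: recipient | pharmacies | communities |
| Distributed doses: source | manufacturer and Public Health | manufacturer |
| Distributed doses: census | 2016 | 2011, and 2016 when available |

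**Algebra.** None of these quantities is given in the documents. Let G be the true gain in points, d the share of G given in pharmacies, s the points switching from physician to pharmacist, and r the pharmacy clients divided by eligible residents. If pharmacists and physicians are the only vaccinators:

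- change in 6.2's second estimate = (1 − d)G − s
- change in 3.1's combined estimate = G
- change in the pharmacy-database estimate = (dG + s)/r, with the client count held fixed

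**Illustration without switching: G = 10, s = 0.**

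| d | 6.2 second estimate | 3.1 combined |
|---|---|---|
| 0.50 | 0.50 × 10 = +5 | +10 |
| 0.75 | 0.25 × 10 = +2.5 | +10 |
| 1.00 | 0 × 10 = 0 | +10 |

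**In doses.** Section 3.1 gives about 30,000 adults per community. Assume physician coverage of 6% before and after, and pharmacist coverage rising from 2% to 12%. That is 0.10 × 30,000 = 3,000 more doses. The combined estimate goes from 8% to 18% (+10), and the physician-only estimate stays at 6% (0).

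**With switching.** Assume pharmacist coverage rises from 2% to 22% while physician coverage falls from 6% to 1%. Combined: 23% − 8% = +15. Physician-only: 1% − 6% = −5. The formula agrees: G = 15, d = 1, s = 5 gives 0 − 5 = −5. The one-for-one fall applies to administered doses such as billing. Public health provision is supply and follows only if supply tracks use, and 6.2 does not say how the two are combined.

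**The other estimates in 6.2.** The pharmacy-database estimate registers pharmacist doses, but it also rises by 1/r per switched point with no true gain: 1.25 at r = 0.8, 0.8 at r = 1.25. This is an upper bound, because a switcher who becomes a new client also enters the denominator. Community-wide distributed doses are unmoved by switching only if the source captures both supply channels. The survey is unmoved only if the mix of respondents does not change.

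**Limit of the combined estimate.** Section 3.2 recognises vaccine-providing nurses. If they give a share n of the gain outside physician reporting, the combined estimate shows (1 − n)G, not G.

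**The case against.** The strongest reply is that this is one combined document and 6.2 should be read with 3.1. Section 3.1 commits to calculating the pharmacist-plus-physician total, and nothing in 6.2 withdraws it. The Synopsis and 3.1 list physician reports as one source among four, so the 6.2 wording may be an incomplete restatement or a component meant to be added to pharmacy doses. The other three estimates in 6.2 can all register pharmacist doses. The mismatch would be decisive only if this estimate decides the primary outcome, and the removed appendices may settle that.

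Most of this stands, and it limits the weight of the point. It does not remove the mismatch: 6.2 presents the physician-only figure as an estimate of coverage in its own right, and its list contains no counterpart to 3.1's administered doses from both providers over the census population.

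A reader might infer that the primary coverage analysis as a whole cannot detect the intervention's effect. The documents do not support that, for the reasons just given. A reader might also infer that 3.1's combined estimate is exact, or that distributed doses and the survey are immune to provider switching. Both depend on the conditions stated in the working.

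**Conclusion.** The point holds as a reconciliation gap that should be fixed; it does not invalidate the primary outcome. That 6.2's second estimate names no pharmacist doses, and that the distributed-dose definitions differ in three respects, is plain from the text. The direction of the consequence follows by algebra: the physician-only figure misses whatever part of a gain pharmacists deliver, and tends to fall with switching.

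The size is not known. The shortfall of 5, 7.5 or 10 points out of a 10-point gain rests on assumed provider shares, no switching, and no vaccinators other than pharmacists and physicians. Confidence is high on the mismatch and lower on its effect on the trial's conclusion, because the estimate that decides may be named in text that is not public.

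**What to change.** - In 6.2, define the second estimate's numerator as pharmacist plus physician doses, as in 3.1, plus doses given by other vaccine-providing nurses where existing sources capture them.
- Use one stated census basis, and the same sources before and after in all four communities. If the study-specific notification forms have no pre-program values, use a physician source that covers both periods and keep the forms as a supplement.
- Report the physician-only figure as a component, not as coverage.
- Define distributed doses identically in both sections: community-wide, from the manufacturer and Public Health, as a supportive estimate. Adopting the 6.2 wording unchanged could drop the Public Health source.
- Label pharmacy doses over pharmacy clients as pharmacy uptake.
- Unless the appendices already do so, state in advance which estimate decides the primary outcome.

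The cost is mainly wording, since the main sources are already in the plan. Three downsides should be stated. People may be counted twice across unlinked sources. Doses from non-participating pharmacies or other providers may be missed: if only participating pharmacies supply data, m points moving to them from non-participating pharmacies raise the combined estimate by m with no true gain. Distributed doses and the survey serve as checks, but survey respondents are self-selected and recruited partly through pharmacies (Section 3.2).

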- 2. To determine pre- and post-intervention knowledge, attitudes, beliefs and behaviours (KABB) of target adults, pharmacists, physicians, and vaccine providing nurses.

Secondary Objectives:

- 1. To assess the impact of various funding models on vaccination coverage.
- 2. To evaluate a pharmacy-based strategy for recruiting participants for a patient-reported active adverse event following immunization surveillance system.

Primary Hypothesis:

 Vaccine coverage with all studied vaccines will increase significantly after implementation of the bundled pharmacist-delivery strategy. A significant increase will be defined as an increase of ≥10% vaccine coverage from pre-program levels.

Secondary Hypotheses:

1. The cost of a vaccine is a key factor in an individuals' decision-making

ROMEO File #: 1021559

with respect to vaccination. It is expected that vaccinations provided at no or minimal charge will have higher uptake than those that require more financial resources to obtain.

2. We hypothesize knowledge about the vaccines studied, high dose TIV, meningococcal B vaccine, meningococcal ACWY vaccine, and Tdap, is low among the general public, but high among practitioners. We hypothesize we will find a high level of support among both the public and health care providers for pharmacists to provide vaccines measured in our study. Knowledge and support amongst both providers and the public will increase after implementation of the program.

Study Methodology

design

This will be a two-year demonstration program implementation and evaluation project in two Canadian provinces, New Brunswick and Nova Scotia. One community in each province will be allocated to implementation strategies specifically designed for each of the target vaccines. One community in each province will serve as the non-intervention control arm where pharmacist immunization practice will continue unchanged.

Inclusion criteria for the selection of the four communities are a stable population, service by a regional hospital and community pharmacies, and lack of substantial health care spill-over to adjacent communities. Spill over is defined as a pattern of health-care utilization where patients regularly receive care at different regional health centres. Communities will be geographically separated to minimize potential spill over.

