Vaccine coverage (number vaccinated divided by the number eligible for vaccine) will be measured using pharmacy database analysis, public health vaccine reports by physicians, vaccine doses delivered (in all four regions), and by public survey within the study communities (part of the KABB survey). Statistics Canada census data from 2015 will be used to determine the denominator for those eligible for the vaccine by 5-year age groups.

3. Adverse Events Following Immunization Reporting (AEFI)

Using the Canadian National Vaccine Safety Network (CANVAS)'s surveillance system for adverse events following seasonal influenza vaccination, we will compare the proportions of eligible individuals who register for CANVAS and complete the online AEFI survey among pharmacies using active recruitment strategies (e.g., handing out information sheets and registration forms) and those using passive recruitment strategies (e.g., displaying posters and information sheets).

Sample Size
 There are four communities involved in the study, Saint John and Moncton, New Brunswick and New Glasgow/Pictou/Antigonish and Kentville/Wolfville/New Minas, Nova Scotia. All participating pharmacies in each community will be allocated either to the bundled pharmacist-delivery intervention or to standard care (control arm). Residents in each community will receive a KABB survey, regardless of whether or not they were vaccinated as part of this study. Information and registration forms

ROMEO File #: 1021559

for CANVAS surveillance will be actively distributed to those who received influenza vaccines in the intervention communities and information on CANVAS will be displayed at pharmacies in control communities. A sample size of 400 for the KABB survey will provide a margin of error of less than 5% for estimated proportions. For vaccine coverage, a separate sample size of 596 per group will provide power of at least 80% to detect superiority.

Endpoints Outcomes/analysis plan/sample size/statistics Outcomes

- 1. Population-specific vaccine coverage before and after programimplementation interventions.
- 2. Proportion of population in intervention districts whose supplementary health benefit plans cover studied vaccines.
- 3. Public KABB about vaccine-preventable diseases and related vaccines before and after program-implementation interventions.
- 4. Public willingness to pay and co-pay for studied vaccines.
- 5. Healthcare providers KABB regarding pharmacist- delivered vaccine programs.

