1.2 Recommended and Funded Vaccines

Tdap and influenza vaccines are recommended and funded for adults in most provinces; however, uptake of these vaccines remains low according to the Public Health Agency of Canada (PHAC). Increases in influenza vaccination rates amongst adults have stagnated and Tdap coverage amongst adults is estimated to be well under 10% (Public Health Agency of Canada, 2015).

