Based on this inclusion criteria, four communities were selected. Intervention communities in which the communication and payment strategies will be implemented are: Saint John, New Brunswick and New Glasgow/Pictou/Antigonish, Nova Scotia area, which include the smaller towns of Stellarton and Westville, Nova Scotia. Control communities where pharmacy delivered immunizations will be offered under their current model are: Moncton, New Brunswick and Kentville/New Minas/Wolfville, Nova Scotia, which include the smaller towns of Canning and Coldbrook, Nova Scotia. Intervention and control communities will be compared to one another to assess the effectiveness of the bundled strategies.

Payment mechanisms will be applied in intervention communities, excluding no client from this strategy. Communication strategies will be targeted based on the type of vaccine a client is eligible to receive. Pharmacists will contact clients over the age of 65 by phone or mail out to recommend high-dose TIV and contact clients who are 50 and older to recommend herpes zoster. Clients who are immunosuppressed may also receive phone calls/mail outs for vaccines against meningococcal disease. Individual eligibility will also be assessed by pharmacists during consultations. Through client's interaction to fill prescriptions, pharmacists have regular contact with high-risk individuals and are able to proactively and systematically review patients' medical histories and medications to remind them of the benefits of specific vaccinations. They can also implement awareness campaigns during travel season and school breaks to target clients who may be travelling to high-risk areas and should consider getting vaccinated to protect themselves against travel-related illnesses, such as Hepatitis A and Typhoid Fever.

Measurement of vaccine coverage

Vaccine coverage rates will be measured using the following:

- **1.** pharmacy database analysis,
- 2. public health vaccine reports by physicians,
- 3. number of vaccine doses delivered to pharmacies in all four regions, and
- 4. public survey within the study communities to determine immunization status.

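### The 80% power and the individual-level tests in section 6.2 do not carry over to a comparison of two communities with two, because only within-family dependence is allowed for.

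*Combined protocol and SAP*

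**What the plan says.** The synopsis sets the unit of allocation: "One community in each province will be allocated to implementation strategies specifically designed for each of the target vaccines". The other community in each province is the control, and all participating pharmacies in a community share its arm. That gives two intervention and two control communities.

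The primary hypothesis (section 2.3) is a pre-to-post rise: "A significant increase will be defined as an increase of ≥10% vaccine coverage from preintervention levels". Section 3.1 adds a second comparison under primary objective 1: "Intervention and control communities will be compared to one another to assess the effectiveness of the bundled strategies".

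For coverage, section 6.2 sets a 10-point superiority margin and states: "when comparing two coverage proportions within site or between sites, a sample size of 298 per group gives 80% power". This is for a true difference of 20 points; for 15 points the figure is 1209. Both are doubled, to 596 and 2418, for two-adult families with full concordance. The synopsis repeats the claim without saying which comparison it covers: "For vaccine coverage, a separate sample size of 596 per group will provide power of at least 80% to detect superiority".

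On analysis, section 6.2 says that "coverage will be compared between and among sites using confidence intervals for the difference of binomial proportions, Fisher's exact tests, and logistic regression". Intraclass correlations are to be estimated, and "these will be used to adjust confidence intervals and test statistics to accommodate within family dependence". The available text has no term for variation between communities. Appendices A to E were removed from the public document and cannot be checked.

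**The concern.** The intervention differs only between communities, so an intervention-versus-control comparison has two independent units per arm, however many residents are counted. Towns differ in coverage and in its trend for reasons unrelated to the programme. That variation does not shrink as more residents are added. A binomial interval, Fisher's exact test or logistic regression on residents leaves it out, and a family-level adjustment does not restore it.

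Two things follow. The between-arm tests reject too often, and more so in larger samples. That matters here because some of the coverage measures use pharmacy databases or census denominators, where counts run far above 596. And the stated 80% power is not a property of the comparison that section 3.1 uses to judge effectiveness. The results are meant to inform public funding decisions, so an ordinary difference between two pairs of towns could be credited to the programme.

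**Working it through.** **Inputs from the documents.** Margin 10 points; true differences of 20 and 15 points; power 80%; 298, 1209, 596 and 2418 per group (section 6.2); two communities per arm (synopsis, section 3.1).

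**Assumptions.** No alpha is stated for coverage; one-sided 5% is inferred because it reproduces the plan's figures. A group is read as an arm pooling two communities. The community SD, s, is not given; 0, 2.5 and 5 points are shown. Near 50% coverage an SD of 5 points is an intraclass correlation of about 0.01 (0.05² / 0.2475).

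**1. The plan's own figures.** n per group = (1.645 + 0.842)² × (p1q1 + p2q2) / (d − 0.10)².

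- 40% v 60%: 296.8, so 297 (plan: 298).
- 42.5% v 57.5%: 1208.7, so 1209 (plan: 1209).
- One-sided 2.5% would give 377 and 1535.

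Full concordance in couples gives a design effect of 1 + (2 − 1) × 1 = 2, hence 596 and 2418. The individual-level arithmetic is sound.

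**2. Rejection rate of the family-adjusted test at the margin.** True difference 10 points, 45% v 55%, concordant couples. The test uses se² = 2(p1q1 + p2q2)/n. The arm difference also has community variance s²/2 + s²/2 = s². So

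rejection rate = 1 − Φ(1.645 × se / √(se² + s²)).

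At n = 596, se = √(2 × 0.495/596) = 4.08 points. With s = 5 the true standard error is √(4.08² + 5²) = 6.45, and 1.645 × 4.08/6.45 = 1.04, giving 15%.

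| Community SD | 596 per arm | 2418 | 10,000 |
|---|---|---|---|
| 0 | 5% | 5% | 5% |
| 2.5 points | 8% | 15% | 27% |
| 5 points | 15% | 27% | 37% |

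At low coverage (7% v 17%, assumed because section 1.2 says "Tdap coverage amongst adults is estimated to be well under 10" per cent) and an SD of 2.5, the rates are 12%, 22% and 34%. If the variance is doubled but responses are in fact independent, the rate at 596 and SD 5 is 12%.

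**3. Power of a valid test at one time point.** 40% v 60%, 596 per arm, t test on four community values (2 df, critical t 2.920). V = s² + 2(0.24 + 0.24)/596; noncentrality = 10/√V, with √V in points.

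- s = 0: √V = 4.01, noncentrality 2.49, power 50%.
- s = 2.5: √V = 4.73, noncentrality 2.11, power 41%.
- s = 5: √V = 6.41, noncentrality 1.56, power 28%.

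A noncentrality of 2.49 gives 80% against the normal critical value of 1.645. With 2 df it gives 50%, before any community variation is assumed.

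**4. Power of a change-score comparison.** Net difference 20 points from a 40% baseline, independent pre and post samples, s now the SD of community change. V = s² + 2(0.24 + 0.24)/m for m residents per community per wave. Critical t is 2.920 (2 df) or 6.314 (1 df, paired by province).

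| m, df | s = 0 | s = 2.5 | s = 5 |
|---|---|---|---|
| 298, 2 df | 33% | 30% | 23% |
| 298, 1 df | 22% | 20% | 17% |
| 5,000, 2 df | 99% | 72% | 37% |
| 5,000, 1 df | 74% | 42% | 24% |

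**5. Limit with unlimited residents.** 80% power needs a noncentrality of 3.98 (2 df) or 8.19 (1 df). At a true 20 points, s can be at most 10/3.98 = 2.5 points or 10/8.19 = 1.2. At 15 points the limits are 5/3.98 = 1.3 and 5/8.19 = 0.6.

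Simulation with concordant couples (200,000 replicates) agreed within about one percentage point.

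**The case against.** The primary hypothesis is a rise within a community, the study calls itself a demonstration programme, and the within-community power figures are not refuted here. All of that is true. But section 6.2 itself extends the power claim to comparisons between sites, and section 3.1 gives the between-community comparison a role in judging effectiveness. If that result is meant as descriptive, the plan should say so rather than specify tests and power.

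The error rates in step 2 apply when the true difference already equals the margin. With no true difference, an SD of 5 and coverage near 50%, the margin test rejects only 0.5% of the time at 596 per arm and 1.1% at 10,000. So a wholly ineffective programme would seldom pass the margin test at these SDs. The margin is nevertheless the plan's null boundary, and tests against zero fare much worse: a two-sided 5% family-adjusted test with no true effect rejects 21% of the time at 596 and 70% at 10,000.

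The change-score powers also depend on testing net change against the 10-point margin. Against zero, the 37% in step 4 becomes 78%.

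The community SD is assumed. The only community SDs in the documents, 28.0 and 18.4 points in section 1.6, come from small rural communities, are not SDs of change and include sampling noise, so they serve at most as an upper guide. The direction of the error is certain; its size is not.

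If a between-site comparison means one community against one other, the 2-df results do not apply. Community and intervention are then fully confounded, and the community variance cannot be estimated at all.

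Finally, a community's own pre-to-post change also carries a local trend. Power for that comparison is power to detect a change, not an intervention effect.

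**Conclusion.** The concern holds, and the text is wrong as written. The figures 298, 1209, 596 and 2418 are correct individual-level sample sizes, and the doubling is a correct worst case for couples. They do not give 80% power for two communities against two. At 596 per arm and a true 20-point difference, a valid single-time-point test has 50% power with no community variation, and that result needs no assumed SD. It rests on the inferred one-sided 5% alpha and on reading a group as an arm of two communities.

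The inflated rejection rates, 8% to 15% at 596 per arm and 27% to 37% at 10,000 in place of 5%, rest in addition on assumed community SDs of 2.5 to 5 points. This should be corrected before any between-arm result is reported as a test.

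**What to change.** In section 6.2 and the synopsis:

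1. Limit the 298/596/1209/2418 and 80% power statements to within-community comparisons, and state the alpha and what a group is. Say that the doubling is the worst case for two-adult family dependence only and omits community-level variation. Add that within-community power is for detecting a change, which may include a local trend.
2. For intervention versus control, report each community's pre-to-post change and the intervention-minus-control difference in change by province. Give an interval from the community-level values with its degrees of freedom (2 unpaired, 1 paired by province), or label the result descriptive.
3. Do not present individual-level Fisher or logistic p-values as tests of the intervention effect. They may describe differences between the named communities if labelled so.
4. State that between-arm power is not established at 80% and depends on an unknown SD of community change, and show a range such as 0, 2.5 and 5 points.

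The cost is rewording plus a small community-level analysis, with no new data. The stated power becomes less favourable and the between-arm intervals become wide, very wide with 1 df, so the between-arm result may end up descriptive only.
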